8.3 Reasons for Removal From Treatment, or Study

8.3.1 Reasons for Removal From Treatment

Reasons for removal from protocol-required investigational product(s) or procedural assessments include any of the following:

- subject request
- safety concern (eg, due to an adverse event, ineligibility determined, protocol deviation, non-compliance, requirement for alternative therapy, pregnancy)
- death
- lost to follow-up
- decision by Sponsor (other than subject request, safety concern, lost to follow-up)

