7.2.3 Treatment

Visits will occur per the Schedule of Assessments (Table 1) during the treatment period from day 1 (baseline) through week 24. On-study visits may be completed within ± 5 days of the target visit date. Prior to enrollment, subject eligibility must be confirmed with screening procedures. Subjects satisfying eligibility requirements will be enrolled. The date of the first dose of etanercept is defined as day 1 (baseline). All subsequent doses and study visits will be scheduled based on the day 1 date.

Etanercept is to be administered at the site after all assessments have been done for all visits that will include dosing. Subjects ending the study prior to week 24 will be asked to complete the unscheduled early termination (ET) visit assessments which are the same as those listed in the Schedule of Assessments under Week 24/ET.

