The sponsor is the exclusive owner of any data, discoveries, or derivative materials from the sample materials and is responsible for the destruction of the sample(s) at the request of the subject through the investigator, at the end of the storage period, or as appropriate (eg, the scientific rationale for experimentation with a certain sample type no longer justifies keeping the sample). If a commercial product is developed from this research project, the sponsor owns the commercial product. The subject has no commercial rights to such product and has no commercial rights to the data, information, discoveries, or derivative materials gained or produced from the sample. See Section 11.3 for subject confidentiality.

8. WITHDRAWAL FROM TREATMENT, PROCEDURES, AND STUDY 8.1 Subjects' Decision to Withdraw

Subjects have the right to withdraw from the study at any time and for any reason without prejudice to their future medical care by the physician or at the institution.

Subjects (or a legally acceptable representative) can decline to continue receiving investigational product and/or other protocol-required therapies or procedures at any time during the study but continue participation in the study. If this occurs, the investigator is to discuss with the subject the appropriate processes for discontinuation from investigational product or other protocol-required therapies and must discuss with the subject the options for continuation of the Schedule of Assessments (Table 1) and collection of data, including endpoints and adverse events. The investigator must document the change to the Schedule of Assessments (Table 1) and the level of follow-up that is agreed to by the subject (eg, in person, by telephone/mail, through family/friends, in correspondence/communication with other physicians, from review of the medical records).

Withdrawal of consent for a study means that the subject does not wish to receive further protocol-required therapies or procedures, and the subject does not wish to or is unable to continue further study participation. Subject data up to withdrawal of consent will be included in the analysis of the study, and where permitted, publically available data can be included after withdrawal of consent. The investigator is to discuss with the subject appropriate procedures for withdrawal from the study.

8.2 Investigator or Sponsor Decision to Withdraw or Terminate Subjects' Participation Prior to Study Completion

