The investigator and/or sponsor can decide to withdraw a subject(s) from investigational product and/or other protocol-required therapies, protocol procedures, or the study as a whole at any time prior to study completion.

Subjects may be eligible for continued treatment with Amgen investigational product(s) and/or other protocol-required therapies by a separate protocol or as provided for by the local country's regulatory mechanism, based on parameters consistent with Section 12.1.

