8.3.2 Reasons for Removal From Study

Reasons for removal of a subject from the study are:

- decision by sponsor
- withdrawal of consent from study
- death
- lost to follow-up

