12.4 Investigator Responsibilities for Data Collection

The investigator is responsible for complying with the requirements for all assessments and data collection (including subjects not receiving protocol-required therapies) as

stipulated in the protocol for each subject in the study. For subjects who withdraw prior to completion of all protocol-required visits and are unable or unwilling to continue the Schedule of Assessments (Table 1), the investigator can search publically available records [where permitted]) to ascertain survival status. This ensures that the data set(s) produced as an outcome of the study is/are as comprehensive as possible.

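### Protocol Sections 8.2 and 8.3.1 allow efficacy assessments to be ended along with the drug, contrary to Section 12.4, so some avoidable missing PASI may be related to outcome

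*Protocol*

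**What the plan says.** Protocol Section 8.3.1 is headed as removal from treatment, but its lead sentence is wider: "Reasons for removal from protocol-required investigational product(s) or procedural assessments include any of the following". One entry on the list is "safety concern (eg, due to an adverse event, ineligibility determined, protocol deviation, non-compliance, requirement for alternative therapy, pregnancy".

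Section 8.2 is consistent with that and is permissive: "The investigator and/or sponsor can decide to withdraw a subject(s) from investigational product and/or other protocol-required therapies, protocol procedures, or the study as a whole".

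Section 8.3.2, introduced by "Reasons for removal of a subject from the study are", lists only sponsor decision, withdrawal of consent, death and loss to follow-up.

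Three other places favour continued collection:
- Section 12.4 makes the investigator responsible for "all assessments and data collection (including subjects not receiving protocol-required therapies".
- Section 8.1, on a subject who declines drug, says the investigator "must discuss with the subject the options for continuation of the Schedule of Assessments (Table 1) and collection of data, including endpoints and adverse events".
- Section 7.2.3 provides that "Subjects ending the study prior to week 24 will be asked to complete the unscheduled early termination (ET) visit assessments". In Table 1 that visit includes PASI, sPGA, BSA and the patient-reported outcomes.

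SAP Section 9.3.2 fills missing efficacy data by LOCF from post-baseline values only. It adds NRI for PASI 75 at Week 12. Observed cases are the other sensitivity analysis for all efficacy endpoints (SAP Section 10.4).

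**The concern.** A site can follow 8.3.1 and fall short of 12.4, and the protocol does not say which governs. The provisions that favour collection leave a gap. The Section 8.1 discussion is required when the subject declines drug or procedures, not when the investigator or sponsor makes the decision. The ET visit belongs to subjects ending the study, and the SAP definition of End of Study Date also links it to premature study withdrawal. Someone removed from drug and assessments, but not from the study, falls between the two.

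The gap matters if the reason for removal is related to response. Section 6.6 bars other systemic psoriasis therapy, phototherapy and most topical treatment during the study, so a subject who needs alternative therapy may well be one whose psoriasis is uncontrolled. SAP Section 9.4 itself names major deviations, dosing compliance and reasons for early withdrawal as possible sources of bias. The further analyses it offers are optional, and they cannot recover scores that were never taken. The study exists to estimate a response rate, so avoidable missing PASI bears on its main product.

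**Working it through.** **Inputs.** N = 80 and an assumed PASI 75 rate of 40% (Protocol Section 10.2), so 32 responders. Precision target: 95% CI half-width below 15%, lower bound above 10% (same section). Neither document gives a dropout or removal rate, so the number m of subjects who lose Week 12 PASI is an assumption.

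**The plan's own figure.** Wald half-width = 1.96 × √(0.40 × 0.60 / 80) = 10.7 points, CI 29.3% to 50.7%. The exact interval for 32/80 is 29.2% to 51.6%, half-width 11.2 points. The precision claim reproduces. The exact lower bound passes 10% from 15 responders of 80 upward.

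**Scenario.** All m subjects are true Week 12 non-responders, and each has at least one post-baseline PASI. Full collection would give 32/80 = 40.0%.

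- Observed cases: 32 / (80 − m).
- LOCF: (32 + k) / 80, where k is the number whose carried PASI is a 75% response. Each such subject adds 1/80 = 1.25 points.
- NRI: 32/80, because missing counts as non-response.

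| m | Observed cases | LOCF, k = 0 | LOCF, k = m/4 | LOCF, k = m/2 | NRI |
|---|---|---|---|---|---|
| 4 | 32/76 = 42.1% | 40.0% | 41.25% | 42.5% | 40.0% |
| 8 | 32/72 = 44.4% | 40.0% | 42.5% | 45.0% | 40.0% |
| 12 | 32/68 = 47.1% | 40.0% | 43.75% | 47.5% | 40.0% |

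The observed-case rise is 2.1, 4.4 or 7.1 points. The LOCF rise runs from zero to 2.5, 5.0 or 7.5 points, depending wholly on k.

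**Limits of the scenario.** A removed subject with no post-baseline PASI has nothing to carry, since baseline is not carried forward, and would not contribute a LOCF value. NRI is exact here only because the lost subjects are taken to be non-responders. If 8 were lost and 40% of them were true responders, NRI would read (32 − 3.2)/80 = 36.0%.

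**Other endpoints.** NRI is planned only for PASI 75 at Week 12. PASI 50 and 90, sPGA, BSA and all other visits have LOCF and observed cases alone.

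**The case against.** Four points can fairly be made against this.

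1. A reader might infer that Week 12 PASI goes missing by rule. The documents do not support that. Section 8.3.1 joins drug and assessments with *or*, Section 8.2 is permissive, and 12.4 points towards collection. The defect is a conflict between sections, not an instruction to stop assessing.
2. A reader might also infer that subjects removed for any listed reason are failing. Nothing in the documents ties protocol deviation, non-compliance or ineligibility found later to non-response. These items are also examples within a safety concern, not free-standing grounds. Only the need for alternative therapy carries a plausible link, and that link is an inference.
3. The table shows no bias in the primary estimate as such. Subjects who are failing would usually carry forward a non-response, which leaves LOCF at 40.0%. It moves only if they had reached PASI 75 earlier. The certain rise is confined to observed cases, a sensitivity analysis, and NRI for the primary endpoint removes it.
4. The affected group is narrow. If the sponsor takes the subject off the study altogether, 8.3.2 covers it and the ET visit applies. An ET visit on Study Day 71 to 98 can serve as Week 12 (SAP Appendix A).

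All four stand and limit the size of the point. They do not remove the conflict between 8.2/8.3.1 and 12.4, the missing ET trigger, or the lack of NRI beyond the primary endpoint.

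A further caution concerns the remedy. Continued assessment will record PASI in some subjects who have started a therapy proscribed in Section 6.6, and neither document says how that PASI is analysed. NRI as the SAP defines it fills only missing values, so all three analyses could credit another treatment's response to etanercept.

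**Conclusion.** The concern holds in a limited form. The protocol permits, but does not require, efficacy assessments to be ended for reasons that are not grounds for leaving the study. That conflicts with 12.4 and leaves some subjects without a clear final PASI. The resulting missing data would be avoidable and may be related to outcome.

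Size rests on assumed numbers: 4 to 12 of 80 subjects lost, all non-responders. On that basis observed cases overstate by 2.1 to 7.1 points. LOCF overstates by 1.25 points per carried response and by nothing if there are none. NRI at Week 12 is unaffected.

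A reader might fear for the conclusion that the etanercept effect is real. The 10% benchmark is not at risk: the lower bound at the planned rate is about 29%. What is exposed is the accuracy of the estimated rate and, more, of the secondary endpoints that have no NRI.

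**What to change.** **Protocol.**
- Delete 'or procedural assessments' from the lead sentence of 8.3.1 and align the mention of 'protocol procedures' in 8.2, so that both agree with 12.4. Editing 8.3.1 alone would leave the same permission in 8.2.
- State that removal from investigational product does not by itself end scheduled assessments, which continue to Week 24 unless the subject declines them or an 8.3.2 reason applies.
- In 7.2.3, ask any subject who stops assessments, for whatever reason, to complete the Week 24/ET assessments at that time.

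**SAP.** Flag PASI collected after proscribed psoriasis therapy and do not count it as an etanercept response. For example, treat it as non-response for PASI 75 and report the as-observed values as a sensitivity analysis.

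None of this sets or changes a rule on when drug is stopped or what other therapy is given.

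**Cost.** Wording in three protocol sections, a few visits by subjects no longer on drug, and one added analysis rule. The visits are already in Table 1 and 12.4 already expects them.

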8.3.2 Reasons for Removal From Study

Reasons for removal of a subject from the study are:

- decision by sponsor
- withdrawal of consent from study
- death
- lost to follow-up

9. SAFETY DATA COLLECTION, RECORDING, AND REPORTING

9.1 Definition of Safety Events

9.1.1 Disease Related Events

Disease Related Events are events (serious or non-serious) anticipated to occur in the study population due to the underlying disease. Disease related events for the purposes of this study include worsening of the skin symptoms associated with PsO. Such events do not meet the definition of an Adverse Event unless assessed to be more severe than expected for the subject's condition.

Disease Related Events and/or Disease Related Outcomes that do not qualify as Serious Adverse Events:

- An event which is part of the normal course of disease under study (eg, disease progression in oncology or hospitalization due to disease progression) is to be reported as a Disease Related Event.
- Death due to the disease under study is to be recorded on the Event CRF.

If the outcome of the underlying disease is worse than that which would normally be expected for the subject, or if the investigator believes there is a causal relationship between the investigational product(s)/study treatment protocol required therapies and disease worsening, this must be reported as an Adverse Event or Serious Adverse Event.

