9.1.3 Serious Adverse Events

A serious adverse event is defined as an adverse event that meets at least 1 of the following serious criteria (unless it meets the definition of a Disease Related Event as defined in Section 9.1.1):

- fatal
- life threatening (places the subject at immediate risk of death)
- requires in-patient hospitalization or prolongation of existing hospitalization
- results in persistent or significant disability/incapacity
- congenital anomaly/birth defect
- other medically important serious event

A disease related event as described above is to be reported as a serious adverse event if:

- the subject's pre-existing condition becomes worse than what the investigator would consider typical for a patient with the same underlying condition, or
- if the investigator believes a causal relationship exists between the investigational medicinal product(s)/protocol-required therapies and the event,
- and the event meets at least 1 of the serious criteria above.

An adverse event would meet the criterion of "requires hospitalization", if the event necessitated an admission to a health care facility (eg, overnight stay).

If an investigator considers an event to be clinically important, but it does not meet any of the serious criteria, the event could be classified as a serious adverse event under the criterion of "other medically important serious event". Examples of such events could include allergic bronchospasm, convulsions, blood dyscrasias, DILI (see Appendix A for drug-induced liver injury reporting criteria), or events that necessitate an emergency room visit, outpatient surgery, or urgent intervention.

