10.3.3 Safety Endpoints

Safety endpoints will be summarized descriptively based on the full analysis set. Subject incidence of all treatment-emergent adverse events will be tabulated by system organ class and preferred term. Tables of fatal adverse events, serious adverse events, adverse events leading to withdrawal from investigational product, and significant treatment-emergent adverse events will be provided.

Subject incidence of disease related events and fatal disease related events will be tabulated by system organ class and preferred term.

Laboratory parameters and vital signs will be summarized by study visit. Shift tables of the worst on-study laboratory toxicity based on CTCAE version 4.0 relative to baseline will be tabulated. Subject listings of grades 3 and 4 laboratory toxicities will be provided.

11. **REGULATORY OBLIGATIONS**

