### 10.5 Safety Analyses

# 10.5.1 Adverse Events

Safety analyses will be conducted using the full analysis set. The Medical Dictionary for Regulatory Activities (MedDRA) version 18.1 or later will be used to code all adverse events (AEs) to a system organ class and a preferred term. Subject incidence of adverse events will be summarized for all treatment-emergent, serious, treatment-related, serious treatment-related, those leading to withdrawal of investigational product, those leading to study withdrawal, and fatal.

The subject incidence of all treatment-emergent, serious, treatment-related, serious treatment-related, those leading to withdrawal of investigational product, those leading to study withdrawal, fatal, and fatal treatment-related adverse events will be tabulated by system organ class and preferred term in descending order of frequency.

A summary of all treatment-emergent adverse events occurring in at least 5% of the subjects will be provided by preferred term in descending order of frequency.

Subgroup analyses by age group (< 65,  $\geq 65$ ), sex (male, female), race (White, non-white) may be presented for AEs summarized by system organ class and preferred term in descending order of frequency.

Subject listings of all treatment-emergent, serious, treatment-related, those leading to withdrawal of investigational product, those leading to study withdrawal, and fatal adverse events will be provided.

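### A serious, non-fatal psoriasis worsening judged both expected and unrelated enters no serious-event table, and the SAP plans no table of disease-related events at all

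*Protocol*

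**What the plan says.** Protocol 9.1.1 sets the class: "Disease Related Events are events (serious or non-serious) anticipated to occur in the study population due to the underlying disease". It then names its content for this trial: "Disease related events for the purposes of this study include worsening of the skin symptoms associated with PsO". It separates the class from adverse events (AEs): "Such events do not meet the definition of an Adverse Event unless assessed to be more severe than expected for the subject's condition". Among the events that are reported as DREs and not as SAEs it lists one that is "part of the normal course of disease under study (eg, disease progression in oncology or hospitalization due to disease progression".

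Protocol 9.1.3 defines an SAE as an AE that meets a serious criterion, "unless it meets the definition of a Disease Related Event as defined in Section 9.1.1". A DRE comes back as an SAE if "the subject's pre-existing condition becomes worse than what the investigator would consider typical for a patient with the same underlying condition, or" the investigator believes that study treatment caused the event; in either case a serious criterion must also be met.

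For the output, protocol 10.3.3 states: "Subject incidence of disease related events and fatal disease related events will be tabulated by system organ class and preferred term". Its serious-event table covers AEs.

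SAP Section 6 repeats the protocol's DRE rule and gives DREs a window from first dose to 30 days after the end of treatment. It defines a serious event as an AE or infection meeting a serious criterion. SAP 10.5.1 says: "Subject incidence of adverse events will be summarized for all treatment-emergent, serious, treatment-related", followed by further categories of AE. Neither that section nor the rest of 10.5 mentions DREs, and SAP Section 11 lists no change on this point.

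**The concern.** The third objective is safety and tolerability of etanercept in apremilast failures. Worsening of the skin disease is a relevant outcome there, and a serious one is what a reader would look for in a serious-event table. Whether it is found there depends on two investigator opinions, expectedness and causality, given open-label and without a control arm.

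The protocol splits off fatal DREs but has no tier for serious, non-fatal ones. A reader of the report could not recover that tier from the planned tables. Nor could the AE and DRE incidences be added, because one subject can be in both.

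The SAP raises a second problem. It defines DREs and then plans nothing with them, so a programmer working from the SAP alone would drop tables that the protocol promises.

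**Working it through.** The plan gives no rate or count of DREs, so there is no figure of its own to reproduce on the main point. The check follows four kinds of psoriasis worsening through the definitions (protocol 9.1.1 and 9.1.3; SAP Section 6) to the outputs (protocol 10.3.3; SAP 10.5).

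| Event | Class under the protocol | Protocol 10.3.3 output | SAP 10.5 output if its DRE rule is applied |
|---|---|---|---|
| Mild, expected, unrelated | DRE | All-DRE table | None |
| Serious, non-fatal, expected and unrelated | DRE | All-DRE table, seriousness not shown | None |
| Fatal, expected and unrelated | DRE | All-DRE and fatal-DRE tables | None |
| Serious, judged atypical or related | SAE | SAE table | Serious AE tables and listings |

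The first two rows have the same protocol output. That is the gap.

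**The SAP's two definitions.** The general AE definition in SAP Section 6 counts any occurrence or worsening of a pre-existing condition as an AE. The DRE definition in the same section excludes expected psoriasis worsening from AEs. For the second row of the table, the general definition puts the event in the serious AE tables and the DRE definition puts it in no planned safety table. Two programmers could report different serious-event incidences from the same data.

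**Are the data collected?** Protocol 9.2.1 requires all DREs on the Event CRF, from first dose to 30 days after last dose. The event is therefore recorded. Section 9.2.1 does not list which attributes are completed for a DRE; the attribute list in 9.2.2.1 is for AEs. Whether seriousness is captured for DREs cannot be settled from the documents.

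**Size per subject.** Planned n = 80, so one subject is 1/80 = 1.25%. Exact (Clopper-Pearson) 95% intervals:

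- 0/80 = 0% (0 to 4.5%)
- 1/80 = 1.25% (0.03% to 6.8%)
- 3/80 = 3.75% (0.8% to 10.6%)
- 4/80 = 5.0% (1.4% to 12.3%)
- 5/80 = 6.25% (2.1% to 14.0%)

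The counts are illustrations. If 3 subjects had SAEs and 1 or 2 others had a serious DRE, the combined figure would be 5.0% or 6.25% where the SAE table shows 3.75%. If the only serious event were a DRE, the SAE table would show 0 of 80 where the combined count is 1 of 80.

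**Chance of at least one such event.** With a rate p per subject, the chance is 1 − (1 − p)^80. Protocol 2.2 gives severe rebound after stopping apremilast as 4/1184 = 0.34%, in line with its stated 0.3%. At that rate the expected count is 80 × 0.0034 = 0.27 and the chance is 24%. That event is not the one at issue: its seriousness is not stated, and it followed apremilast withdrawal, not etanercept treatment. Assumed rates of 1%, 2% and 5%, which are not in the documents, give 55%, 80% and 98%.

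**The case against.** Separating disease course from drug harm in advance is a legitimate design choice, and this protocol has safeguards. A flare judged worse than typical, or related, returns to the SAEs once it meets a serious criterion. Active erythrodermic, pustular and guttate disease is excluded at screening, so an admission that still counts as expected is plausibly rare. PASI, sPGA, BSA and PSI are taken at every treatment visit, withdrawal reasons are summarised, and no DRE is lost from the database. Safety is descriptive and no hypothesis is tested, so no planned decision changes.

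Most of this stands, and it limits the size of the point. It does not close the gap, because none of those outputs shows that a worsening was serious, and carrying a last observation forward can hide a late flare in the efficacy data.

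A reader might go further in three ways that the documents do not support.

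- That every hospitalised flare on etanercept is missing from the serious tables. The routes back to SAE status in 9.1.1 and 9.1.3 rule this out; only a flare judged both expected and unrelated is affected.
- That the serious-event incidence will be understated. The rule makes this possible, but no document gives a number of affected subjects.
- That psoriasis worsening is the only harm the protocol anticipates. Section 9.2.2.4 also anticipates SAEs from hypertension, myocardial infarction, depression and other comorbidities.

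**Conclusion.** The point holds in a narrow form. As the protocol is written, a serious, non-fatal psoriasis worsening judged both expected and unrelated is a DRE, enters no serious-event table, and cannot be distinguished from mild worsening in the all-DRE table. The SAP omits DRE tables altogether without declaring it, and its own definitions leave the class of such an event open.

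The effect is 1.25 percentage points per affected subject, assuming 80 treated subjects. The number affected is unknown and probably small, possibly zero. The conclusion rests on the text of the definitions and planned outputs, not on any assumed rate. It is worth correcting before the tables are programmed, but it does not threaten the primary estimate.

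**What to change.** 1. Restore in SAP 10.5 the all-DRE and fatal-DRE tables that protocol 10.3.3 promises, or declare and justify their omission in Section 11.
2. In protocol 10.3.3 and SAP 10.5.1, add the subject incidence of serious DREs and of SAE or serious DRE, each subject counted once, with a listing. Use one window for the combined figure, first dose to 30 days after last dose, because SAEs are collected from consent and DREs only from first dose.
3. Reconcile the AE and DRE definitions in SAP Section 6 so that psoriasis worsening is classified one way.
4. Confirm that the seriousness field on the Event CRF is completed for DREs.

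Deleting the hospitalisation example from protocol 9.1.1 would not help. The exclusion rests on the class covering serious events in 9.1.1 and on the exception in 9.1.3, and both would remain.

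The cost is one or two more tables and a listing, repeated by reason for apremilast failure if SAP Section 11 is followed, plus a small wording change. If item 4 shows that seriousness is not recorded for DREs, sites would have to supply it. The serious-event figure may become slightly less favourable.
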